Belatacept Conversion in Proteinuric Renal Transplant Recipients and B7-1 Positivity Status on Biopsy: an Interventional Multi-Center Trial

Version Date: 09-July-2019

Short Title: B7-1 Study

Institutional (Partners IRB) #2015P000154

NCT02327403 (clinicaltrials.gov)

IND 125511

Sponsor: [name], PhD

Funding Source/Drug Supplier: Bristol-Myers Squibb (BMS)

BMS ISR Protocol number: IM103-363

Study Sponsor/Overall Principal Investigator/IND holder:

[name], PhD

Brigham and Women's Hospital (BWH), Harvard Medical School (HMS)

Transplantation Research Center (TRC), [name]

[name]

Ph: [contact]

[contact]

Email: [contact]

Medical Monitor (MM)/DSMB Chair (available 24/7) :

[name]

[contact]

Study Clinical Research Coordinator/Accounts Payable:

[name]

BWH CCI

[name]

Office [contact]

Central Laboratory [(Transplantation Research Center, (TRC)] Technician:

[name]

Brigham & Women's Hospital

Transplantation Research Center, EBRC

[name]

Office [contact]

[contact]

Email: [contact]

I. Study Synopsis

Background: Proteinuria develops in about 30% of kidney transplant recipients and is a strong predictor of graft loss. The amount of proteinuria has a direct correlation with the risk of graft failure. Novel therapies are urgently needed to reduce proteinuria and prevent graft loss in transplant recipients, since ACE inhibitors carry a number of limitations in the transplant setting, including significant reduction in renal function, anemia and hyperkalemia.

Preliminary data: B7-1 is expressed at significant levels in about 10% of kidney allograft biopsies with predominance in patients with proteinuria.

[figure not shown]
Hypothesis: We hypothesize that B7-1 targeting therapy may reduce proteinuria and improve graft survival in proteinuric transplant recipients that have B7-1 staining on allografts. In addition, the absence of calcineurin inhibitor (CNI) nephrotoxicity and the potential protective effect of Belatacept on DSA production may be of benefit in this subset of transplant patients.

Objectives:

Primary: Determine the effect of Belatacept conversion in reducing proteinuria by 25% at 12 months in renal transplant recipients ($\geq 1\text{gram/d}$) that are either B7-1-positive or negative on kidney biopsy.

Secondary: Assess the effect of Belatacept conversion in the percent change of renal function from baseline to 12 months; donor-specific anti-HLA antibodies presence and intensity (MFI); correlation of B7-1 positivity on immunofluorescence on biopsy with B7-1-expression in urine extracellular vesicles; adverse events; acute rejection episodes; blood pressure control; new onset diabetes; hyperlipidemia; graft survival; and patient survival.

Study design:

Inclusion Criteria:

1. Male or female adult kidney transplant recipients older than 18 years old
2. eGFR $\geq 30\text{ ml/min}$
3. ≥ 6 months after transplantation
4. Proteinuria $\geq 1\text{ gram/day}$ in spot urine protein/creatinine ratio
5. Available biopsy specimen for B7-1 staining at recruitment time.
6. Ability to provide written informed consent for the study.
7. Maintenance immunosuppression of CNI (cyclosporine or tacrolimus), antiproliferative agent (azathioprine, MMF or MPA) with either steroids or not.
8. Must be EBV IgG positive

Exclusion Criteria:

1. Age < 18 years

2. eGFR<30 ml/min
3. active acute cellular rejection (ACR; higher than borderline) or ACR in the previous 6 months; active acute antibody-mediated rejection.
4. recurrent FSGS
5. EBV IgG negative
6. patient on mTOR inhibitor (e.g. Everolimus, Sirolimus)
7. patient only on CNI (cyclosporine or tacrolimus) and steroids

Accrual Goal: 36 subjects, 3 study sites

Accrual Rate: approximately 2 subjects/month; total of 18 months enrollment; 18 months of follow-up

First Patient First Visit: 1-March-2015

Statistics: This is a Phase I clinical trial to test the safety and gain further insight into the potential effect of Belatacept in proteinuric kidney transplant patients. We plan to recruit 36 patients, based on the feasibility for recruitment in 3 transplant centers and prior literature on recommended sample sizes in a Phase I trial.

2. Background:

Although improvements in immunosuppression have led to a reduction in acute rejection rates, long-term allograft survival remains disappointing, with more than 50% of allografts lost 10 years after transplantation.

Proteinuria develops in about **30% of kidney transplant recipients** and is **strong predictor of graft loss** (1-3). The amount of proteinuria has a direct correlation with the risk of graft failure (**Figure 1**). More than 80% of patients with proteinuria greater than 1500 mg/d have evidence of allograft glomerular pathology. Among these, transplant glomerulopathy is the leading etiology in about 45% of cases followed by recurrent glomerular disease (25%) (4, 5). Patients with more than 1 gram/day of proteinuria after transplantation carry a dismal prognosis more than 50% of grafts lost after a mean follow up of 5 years (4). The proteinuria on these patients continues to progress and kidney function deteriorates until grafts are lost with no effective therapy to halt this progression, therefore the need to establish novel therapies for this subset of transplant patients.

KDIGO guidelines recommend ACEI/ARB in post-transplant proteinuric patients though there is no clear evidence that this approach improves renal transplant survival (6, 7). In contrary, ACEI/ARB have been associated with significant decrease in renal function, anemia and hyperkalemia post-transplantation. Novel therapies are urgently needed to reduce proteinuria and prevent graft loss in transplant recipients.

It has been recently published that **Abatacept is able to reduce proteinuria in patients with B7-1-positive glomerular disease** by stabilizing β 1-integrin activation in podocytes (8). However, prevalence of positive B7-1 staining in renal allografts and a possible role of B7-1 target therapy in the treatment of proteinuria post-transplantation remains to be explored.

3. Preliminary Data:

[figure not shown]

Figure 1. Risk of graft failure according to degree of proteinuria.

Using a goat anti-human B7-1 (CD80) antibody, we performed immunostaining for B7-1 on frozen sections of **123 clinically indicated kidney transplant biopsies** obtained between 2011 and 2012. Fifteen patients had $\geq 1+$ B7-1 staining on glomeruli at podocyte location (**Figure 2**). The predominant pathologic diagnosis among those with B7-1 positivity was **transplant glomerulopathy** (46%). In addition, 27% of patients with $\geq 1+$ B7-1 staining in their biopsies had nephrotic range proteinuria (4 out of 15) and 50% of allograft biopsies obtained from patients with nephrotic syndrome stained positive for B7-1 (4 out of 8). In sum, **B7-1 is expressed at significant levels in about 10% of kidney allograft biopsies.**

[figure not shown]

Figure 2. B7-1 staining in kidney transplant biopsies.

4. Hypothesis:

We hypothesize that B7-1 targeting therapy may reduce proteinuria and improve graft survival in proteinuric transplant recipients that have B7-1 staining on allografts. In addition, the absence of CNI nephrotoxicity and the potential protective effect of Belatacept on DSA production may be of benefit in this subset of transplant patients (9, 10).

5. Objectives:

Primary: Determine the effect of Belatacept conversion in reducing proteinuria by 25% at 12 months in renal transplant recipients that have more than 1 gram of proteinuria per day and are either B7-1-positive or negative on kidney biopsy.

Secondary: Assess the effect of Belatacept conversion in the percent change of renal function from baseline to 12 months; donor-specific anti-HLA antibodies presence and intensity (MFI); correlation of B7-1 positivity on immunofluorescence on biopsy with B7-1-expression in urine extracellular vesicles; adverse events; acute rejection episodes; blood pressure control; new onset diabetes; hyperlipidemia; graft survival; and patient survival.

6. Proposal:

We propose to perform a multi-center study in which adult kidney transplant recipients with proteinuria (≥ 1 g/day) will be converted from CNI to Belatacept (**Figure 3**) once B7-1 staining has been performed on allograft biopsy ([name] will be performing all stains). This is a Phase I study that will aim to enroll 36 patients in 18-month recruitment time involving 3 transplant sites. Other inclusion criteria include: eGFR > 30 ml/min, greater than 6 months post-transplant and EBV IgG positive status. **Exclusion criteria** include: age < 18 years, eGFR < 30 ml/min, active acute cellular rejection (ACR; higher than borderline) or ACR in the previous 6 months, recurrent FSGS, EBV IgG negative status and on mTOR inhibitor as maintenance immunosuppression.

[figure not shown]

Figure 3. Study Design. Protocol and outcomes measures are detailed.

Patients that develop proteinuria after transplant are a heterogenous group with many potential

underlying etiologies including calcineurin inhibitor toxicity, transplant glomerulopathy, BK nephropathy or recurrent glomerular disease (4). Therefore, we decided to enroll 12 patients per center (3 centers total) to allow the inclusion of different etiologies of proteinuria and be a feasible study based on our inclusion criteria.

By including both B7-1 positive and B7-1 negative patients with proteinuria in the study, we will have the best chance of success and it would also allow for future testing for other potential prognostic markers in this population. One of the main reasoning's behind this is that the B7-1 staining is undergoing further optimization by [name] and a NIH task force, and therefore, restricting our recruitment may limit interpretation of the data in case the staining changes. This has been previously shown to be most productive approach in biomarker-driven interventions in the cancer field (11). In addition, the exact mechanism in which B7-1 targeting reduce proteinuria is still debated. By including both B7-1 positive and B7-1 negative patients with proteinuria, we will be able to assess overall risk factors and have a control group with no B7-1 staining treated with Belatacept. A historical control group with patients that fit the inclusion criteria and were managed as standard of care at our institution will also be included for comparison.

The **primary endpoint** of the study will be a 25% reduction in proteinuria from baseline to 12 months. This endpoint was extrapolated from studies with ACE inhibitors showing significant benefit in patients with kidney disease and proteinuria that reached this endpoint (12). **Secondary end-points** include: percent change of renal function from baseline to 12 months; donor-specific anti-HLA antibodies presence and intensity (MFI); correlation of B7-1 positivity on immunofluorescence on biopsy with B7-1-expression in urine extracellular vesicles; adverse events; acute rejection episodes; blood pressure control; new onset diabetes; hyperlipidemia; graft survival; and patient survival. At 18 months, we will perform a chart review to check if patient remained or not on Belatacept, their renal function, proteinuria and biopsy-proven rejection events since trial termination.

Developing a **urinary biomarker to non-invasively detect patients with B7-1 expression on allografts** is another goal of this study. This will not only allow monitoring of treatment effectiveness and serving as secondary end-points but will also permit non-invasively screening for B7-1 positivity in patients in the future. Briefly, we will isolate RNA from urinary extracellular vesicles (EVs) of transplanted patients and detect B7-1 mRNA using "Droplet Digital" PCR system. EVs such as exosomes (40-100 nm in diameter) and microvesicles (100-1000 nm) are nanometer-sized vesicles released by cells including kidney podocytes to mediate cell-to-cell communication by delivering proteins and genetic materials such as mRNAs and microRNAs (13). We hypothesize that podocytes expressing B7-1 will shed EVs into the urine that will carry B7-1 mRNA. [name] laboratory at the Transplantation Research Center (Co-Investigator) optimized the isolation of high quality and quantity of RNA from urinary EVs of transplant patients (Figure 4).

Enrolled patients will have serum and urine collected at time of conversion and 12 months post-conversion. Urine will be processed for extracellular vesicles (EVs) and mRNA isolation. Samples will be stored at minus 80 degrees Celsius freezer until analysis. Future alternative approaches for characterization of B7-1 expression on kidney allografts involve determination of urinary B7-1 mRNA

[figure not shown]

Figure 4. A, Electron Microscopy of urinary exosomes from a kidney transplant recipient labeled with exosomal marker, CD63. B, High sensitivity RNA analysis of urinary EVs. Urinary EVs were isolated from urine (average 35 ml) of a kidney transplant recipient followed by RNA isolation Agilent Bioanalyzer RNA for qualitative and quantitative analysis of RNA.

by PCR and laser micro-dissection of glomerulus on biopsy sample followed by measurement of B7-1 by QT-PCR.

Sample size calculation: This is a Phase I clinical trial to test the safety and gain further insight into the potential effect of Belatacept in proteinuric patients. We plan to recruit 36 patients, based on the feasibility for recruitment in 3 transplant centers and prior literature on recommended sample sizes in Phase I trials.(14, 15).

Impact: Causes of long-term graft loss are heterogenous and it is clear that the one-size-fits-all approach in transplantation is deemed for failure. Therefore, we believe that the identification of abnormal B7-1 expression in proteinuric kidney transplant recipients may permit the application of a personalized target therapy that will have a higher likelihood of success, avoiding the use of costly ineffective agents, minimizing their adverse effects and potentially improving long-term graft survival. Lastly, prior work from our laboratory has shown some promising results in B7 targeting in experimental models of chronic allograft rejection (16, 17) and more recent work supports an effective role of B7 targeting in suppressing humoral response through significant reduction in T follicular helper cells (18). Both findings support additional pathophysiological mechanisms involving not only podocytes but the immune system in contributing to obtain favorable results in this proposed study.

Ethical considerations:

All study investigators and study staff must follow all appropriate requirements, including Good Clinical Practice (GCP), International Conference on Harmonization (ICH), Code of Federal Regulations (CFR), and the Partners Human Research Committee (PHRC) Institutional Review Board (IRB). The study will be conducted in compliance of the protocol. The protocol, all amendments, and the subject informed consent will receive Institutional Review Board/Independent Ethics Committee (IRB/IEC) approval/favorable opinion before initiation of the study. Study personnel must be qualified by education, training and experience to perform their respective tasks, and will not utilize personnel for whom sanctions have been invoked or where there has been scientific misconduct or fraud.

Appropriate study personnel will obtain signed and dated informed consent from each study participant. [Investigators will ensure that subjects, or their legally acceptable representatives, are clearly and fully informed about the purpose, potential risks, and other critical issues regarding this clinical research study in which they voluntarily participate. The approved consent form will adhere to the ethical principles that have their origin in the Declaration of Helsinki. All relevant safety information regarding the dose/schedule of study drug, or any other drugs/procedures in this clinical study must be explained in the informed consent document. Informed consent will also delineate which authorities may have direct access to study records and documents. Consent will also clearly state that although [name] is the study sponsor, Bristol-Myers Squibb (BMS) is the study funding source and is also supplying study drug for this study.

7. Eligibility:

7.1 Inclusion Criteria:

- Deceased or living donor adult kidney transplant recipients older than 18 years old
- eGFR >30 ml/min
- >6 months after transplantation
- Proteinuria >1 gram/day in spot urine protein/creatinine ratio
- Available biopsy specimen for B7-1 staining at recruitment time.
- Ability to provide written informed consent for the study.
- Must be EBV IgG positive

7.2 Exclusion Criteria:

- Age <18 years
- eGFR<30 ml/min
- Active acute cellular rejection (ACR; higher than borderline) or ACR in the previous 6 months; active acute antibody-mediated rejection.
- Recurrent FSGS
- EBV IgG negative

- Patient on mTOR inhibitor (e.g. Everolimus, Sirolimus)
- Age and Reproductive Status:

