7.5 LESS EFFECTIVE METHODS OF CONTRACEPTION

- Diaphragm with spermicide

- Cervical cap with spermicide
- Vaginal sponge
- Male Condom without spermicide
- Progestin only pills by WOCBP subject or male subject's WOCBP partner
- Female Condom*.

* A male and female condom must not be used together

8. Study Drug: Belatacept (Treatment with Belatacept will continue for 12 months)**:

Belatacept conversion dosing: 5 mg/kg IV on days 1, 15, 29, 43 and 57, followed by an infusion every 28 days thereafter. Calcineurin inhibitors (CNI) Taper: CNI dose will remain the same for week 1 and then will be tapered by 25% each week and discontinued at the end of week 4 (day 29).

Infusion pre-medications: none

Duration of Infusion: 30 minutes

Observation period post-infusion: none

Standard of Care (SOC) Dosing of Belatacept:

5 x the patient's weight (in kg) = mg of Belatacept. Dose then needs to be rounded to the nearest 12.5 mg increment. Example: 74 kg patient x 5 = 370 mg; rounded to the nearest 12.5 mg increment = 375 mg. At the end of 12 months, study subjects have completed the study drug protocol and they have the option to continue on Belatacept treatment, paid for by their medical insurance, or they can switch back to a CNI.

**Please see additional important study drug information on pages 11-12.

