8.1 Potential Risks of Belatacept

8.1.1 Acute Rejection

Acute rejection is expected to be the principle risk in this study. In quantitative terms, the magnitude of renal function benefit necessary to offset the risk of incremental acute rejection (up to 10% based upon historical experience in the conversion setting) is not well characterized. Further, opinion among treating clinicians may vary based upon a number of factors, including individual patient needs and the clinician's assessment of the relative importance of rejection versus renal function as predictors of long-term outcomes. Thus, it is anticipated that a comprehensive review of the totality of safety and efficacy data will be necessary in order to characterize the clinical importance of acute rejection. The long-term data is reassuring since even patients that developed an episode of acute rejection had improved renal function when compared to CNI regimen at 5 years post-transplant.

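### The two full eligibility lists disagree: only the synopsis requires an antiproliferative agent alongside the CNI; Sections 7.1 and 7.2 do not

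*Combined protocol and SAP*

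**What the plan says.** The protocol contains two full eligibility lists.

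- **Study Synopsis.** Inclusion item 7 reads "Maintenance immunosuppression of CNI (cyclosporine or tacrolimus), antiproliferative agent (azathioprine, MMF or MPA) with either steroids or not". Exclusion item 7 reads "patient only on CNI (cyclosporine or tacrolimus) and steroids".
- **Sections 7.1 and 7.2 (Eligibility).** Section 7.1 has seven inclusion bullets, and none concerns maintenance drugs. The only immunosuppression item in Section 7.2 is "Patient on mTOR inhibitor (e.g. Everolimus, Sirolimus)". Section 7.3 deals with reproductive status.

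Section 8 has the CNI held for week 1, then "tapered by 25% each week and discontinued at the end of week 4 (day 29)". Section 8.1.1 says "Acute rejection is expected to be the principle risk in this study". The Ethical considerations text says "The study will be conducted in compliance of the protocol", but nothing in the document says which list takes precedence if the two differ.

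Sections 6 and 11 add a historical control group, whose members must fit the inclusion criteria. Neither section says which list is meant.

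**The concern.** A patient maintained on a CNI and steroids is excluded by one list and passes the other. If such a patient is enrolled and the CNI is withdrawn on schedule, the remaining regimen is belatacept and steroids, unless someone adds an antiproliferative agent. Section 8 gives no instruction to add one. In a trial whose main expected hazard is rejection after CNI withdrawal, the background cover a patient must have should not depend on which page the site screens from.

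A second, weaker consequence concerns the historical controls. They are not converted, so no taper implies that they were on a CNI. If their selection followed Section 7.1 alone, their maintenance regimen would be unspecified.

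**Working it through.** No power, alpha or sample-size figure is involved, so the check is a comparison of texts.

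**Item count.** The synopsis has 8 inclusion + 7 exclusion = 15 criteria. Inclusion items 1–6 and 8 (7 items) and exclusion items 1–6 (6 items) have counterparts in Sections 7.1 and 7.2: 7 + 6 = 13. The remaining 15 − 13 = 2 are inclusion 7 and exclusion 7, which together express one rule.

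**Effect by baseline regimen**, taking every other criterion as met:

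| Baseline regimen | Synopsis | Sections 7.1–7.2 | After day 29 if nothing is added |
|---|---|---|---|
| CNI + antiproliferative, with or without steroids | Eligible | Eligible | Belatacept + antiproliferative, with or without steroids |
| CNI + steroids | Fails inclusion 7 and meets exclusion 7 | No item bars entry | Belatacept + steroids |
| CNI alone | Fails inclusion 7; exclusion 7 does not literally name it | No item bars entry | Belatacept alone |

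The lists part in the second and third rows. The third row shows why exclusion 7 would not be enough if copied alone.

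**Does other text restore the rule?**

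- *The CNI half:* yes, for treated patients. Section 6 describes conversion from a CNI, and Section 8 and the Schedule of Events taper one.
- *The antiproliferative half:* no. Section 8.1.6 names MMF and MPA among the non-investigational products, but does not make them a condition of entry. It also leaves out azathioprine, which the synopsis accepts.
- *Section 6:* its inclusion summary ("Other inclusion criteria include: eGFR > 30 ml/min, greater than 6 months post-transplant and EBV IgG positive status") and its exclusion summary, which ends "EBV IgG negative status and on mTOR inhibitor as maintenance immunosuppression", do not mention the rule. This carries little weight. The summary is partial and also omits written consent and active antibody-mediated rejection, which both full lists contain.

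**Historical comparison.** The four covariates named in Section 11 are ACEI/ARB use, level of proteinuria, age and gender. None is baseline immunosuppression, although they are introduced as examples and the list is open. The entry criterion is thus the clearest stated means of aligning the regimens of treated patients and controls.

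**Timing.** Planned enrolment was 18 months from 1 March 2015, which gives 1 September 2016. This version is dated 9 July 2019, about 34 months later. Actual accrual is not stated.

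**The case against.** The best reply is that Section 7 is silent and does not contradict the synopsis. The synopsis is part of the protocol with which the study must comply, and both lists can be satisfied at once. A site that applies both would exclude every patient in question. That stands, and it limits the point to a site that screens from Section 7 by itself. It does not remove the point: Section 7 is the section headed Eligibility, and the protocol does not tell sites to combine the lists.

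The controls are also less exposed than they first appear. Inclusion 7 is headed as an inclusion criterion, so on a natural reading it already applies to them. An explicit sentence would only confirm this.

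The Manual of Procedures and the eCRFs are cited but not supplied. An eligibility checklist there might settle the matter, but that cannot be checked.

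On the planned timeline enrolment had closed well before this version, so the copied lines might change no enrolment. That is fair, though the control criterion could still matter for selection and reporting.

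Three stronger readings are tempting, and the documents support none of them:

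- **That converted patients faced a higher rejection risk because of the gap.** Section 8.1.1 cites up to 10% incremental rejection in the conversion setting, but does not break it down by antiproliferative use. Nothing shows that such a patient was enrolled.
- **That rejections short of refractory would go unwatched.** Rejection episodes meet the adverse-event definition in Section 10.2 and can lead to drug discontinuation under Section 9C. They can also reach the DSMB, which meets quarterly, receives safety data and may recommend stopping.
- **That the historical comparison is biased.** The regimen of the controls is not reported, and inclusion 7 most naturally covers them.

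**Conclusion.** The inconsistency is real and minor. The two full lists differ on one rule, expressed in 2 of 15 synopsis criteria. For treated patients the substantive gap is the antiproliferative requirement only. Section 7, applied by itself, admits patients whom the synopsis bars. How many treated patients or controls this touches is unknown and may be zero, and no excess risk can be quantified from the documents.

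The conclusion assumes that at least one site could screen from Section 7 alone, and that no unsupplied document already reconciles the lists. It does not assume that Section 7 overrides the synopsis; the protocol gives neither list precedence.

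**What to change.** 1. Copy synopsis inclusion item 7 into Section 7.1 and synopsis exclusion item 7 into Section 7.2.
2. In Section 11, state that historical controls must meet the same maintenance-regimen criterion at their baseline.

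The cost is two copied lines and one sentence, plus a check of each control's baseline regimen. A few otherwise eligible patients or controls may be lost. The target of 36 stays the same, and no additional analysis is needed.

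This does not make the lists identical. The synopsis uses ≥ and Section 7.1 uses > for eGFR, time since transplant and proteinuria; those signs could be aligned in the same edit.
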